7.5 Contraception and pregnancy

All female participants of childbearing potential should use adequate contraception starting 10 days before each intervention period and during intervention period, such as an oral, injectable, or implantable contraceptives or contraceptive devices (IUP). To minimize the risk of exposure to IMP we will perform a pregnancy test before administration of study drug on test day 1 and 3.

If against all demanded contraception, a pregnancy should occur the pregnant participant must be withdrawn immediately from the clinical study. Any pregnancy during the treatment phase of the study and within 30 days after discontinuation of study medication will be reported to the Sponsor-Investigator within 24 hours.

The pregnancy will be followed-up like an SAE. A document for the initial registration is available, as well as one for the end of the first trimenon. All other relevant information that we should receive from the participant will be documented. Information about course and outcome of pregnancy from the treating gynecologist might be asked after release from the confidentiality by the participant.

A follow-up of mother and child after the first trimenon is not foreseen, as no risks are expected for the development of the unborn thereafter.

8 STUDY INTERVENTION

8.1 Identity of Investigational Products

8.1.1 Experimental Intervention

Active study medication consists of 7 tablets of fampridine 10 mg formulated for oral administration taken in the morning and evening 12 h apart without food. Tablets must be administered whole: do not divide, crush, chew, or dissolve Fampyra® retard tablets.

There will be a washout period of at least 8 days equaling over 30 half-lives of the active substance fampridine ($t_{1/2} = 6$ h) between experimental and control intervention and up to 82 days (12 weeks) depending on the individual scheduling of each subject.

8.1.2 Control Intervention

Identically looking placebo tablets consisting of widely identical additives formulated for oral administration.

8.1.3 Packaging, Labelling and Supply (re-supply)

Packaging, labelling and supply will be provided by the Pharmacy of the University Hospital Basel (see chapter 6.2.2).

8.1.4 Storage Conditions

The IMP will be stored under 25° C and protected from light and humidity until initiation at the pharmacy. Thereafter the IMP will be stored for the entire study until last participant out at the same conditions in our division. The storage temperature will be controlled with LogTag temperature recorder.

8.2 Administration of experimental and control interventions

8.2.1 Experimental Intervention

See chapter 8.1.1

8.2.2 Control Intervention

See chapter 8.1.2.

8.3 Dose

No modifications needed.

8.4 Compliance with study intervention

Each subject will be provided with a personal login to secuTrial® to be able to document the intake of the investigational product at a time. A study team member will send a note if entry is missing to remind the subject of intake of the investigational product.

All subjects have to return the container on the following test days in order to control the container for not used tablets and for correct disposal of remaining tablets after study end.

Blinding is warranted (see chapter 7.6, Randomization and Blinding).

8.5 Data Collection and Follow-up for withdrawn participants

Not needed. Subject withdrawn because of (S)AE will be followed up until resolution or stabilization.

8.6 Trial specific preventive measures

In case of headache, pain or fever, paracetamol is allowed and has to be recorded as concomitant medication.

8.7 Concomitant Interventions (treatments)

Treatments with OCT 2 inhibitors or substrates (e.g. cimetidine, propranolol) are prohibited during the course of the study as they may inhibit elimination of fampridine and increase the risk of adverse events. All concomitant treatment will be recorded in the eCRF.

8.8 Study Drug Accountability

The supplies from and the returns to the pharmacy of the USB for destruction will be documented at the pharmacy and also by the study coordinator on the site in the IMP accountability log. This log documents the IMPs received from the pharmacy, the kits used by each participant, and the return to the pharmacy of used and unused kits.

This documentation includes the following information: delivery date, delivered kits, batch number, expiry date.

The administration of the IMP to the participants is recorded in the participant dossier.

8.9 Return or Destruction of Study Drug

Used and unused kits will be returned to the pharmacy of the USB for destruction. The pharmacy will destroy and dispose them duly in accordance to hospital policy and the local directives.

9 STUDY ASSESSMENTS

9.1 Study flow chart(s) / table of study procedures and assessments

See study schedule (Table 1, Duration of study parts, page 12)

9.2 Assessments of outcomes

9.2.1 Assessment of primary outcome

- High-load working memory performance will be measured as follows: We will use the letter n-back task (Heck, Fastenrath et al. 2014) which includes a 3-back task assessing working memory. The 3-back task requires participants to respond to a letter repeat with two intervening letters (for example, S-m-b-s-g...). Performance will be quantified with the d' measure controlling for false positives. We will use parallel versions (different sequences) for the four test days. Primary outcome will be performance after repeated intake of study medication.

9.2.2 Assessment of secondary outcomes

- High-load working memory performance(see above) after acute intake of study medication.
- Resting motor threshold (rMT) will be measured during screening procedures and after repeated intake with a biphasic magstim Rapid2 stimulator (The MAGSTIM® Company Ltd, Whitland, UK) and a 70 mm figure-of-eight coil.

rMT will be determined by measuring the motor evoked potential (MEP) in the abductor digiti minimi according to (Rossini 2001). rMT will be defined as the lowest stimulation intensity by stimulating the primary motor cortex of the left or right hemisphere required to induce an MEP in the abductor digiti minimi of the dominant hand in at least 5 out of 10 trials. In case of a relaxed target muscle, a positive MEP is defined as an MEP with $\geq 50 \mu\text{V}$ peak-to-peak amplitude (Rossini 2001).

The coil will be held tangentially to the skull over M1, approximately four cm lateral and one cm anterior to the Vertex. Additionally, the coil-handle points backwards at an angle of 45° to the corresponding parasagittal line. Then the coil will be shifted systematically in steps of approximately one cm in anterior, posterior, lateral and medial direction. Stimulation will be performed at an initial output intensity of 30% of maximum stimulator's output (MSO) and will be increased in steps of 10% until a twitch is detected. Thereafter, 10 pulses will be applied. If less than five MEPs are observed, stimulator output intensity will be increased by 5 %. Depending on the result, intensity will be further decreased or again increased by steps of two and then one percent until the lowest stimulator intensity is found. Otherwise stimulator output intensity is first decreased 5% and thereafter increased or decreased by steps of two and then one percent until rMT is found. The participant is always allowed to stop the measuring, if he/she feels ill at ease.

Performance in other working memory-related tasks and other n-back outcomes will be measured both after acute and repeated study medication as follows:

- Reaction time_(for correct 3-back responses).
- Performance in a 0-back task (d' measure controlled) as a measure of attention. We will use parallel versions (different sequences) for the four test days
- Symbol Digit Modalities Test, SDMT (Smith 2013, 13th edition), a processing speed test. The test consists of the presentation of a series of 9 symbols, each of them is paired with a single digit, labelled 1–9, in a key at the top of a sheet. The remainder of the page has a pseudorandomized sequence of the symbols and the participant must respond with the digit associated with each of these as quickly as possible. The score is the number of correct answers in 90 seconds. The administration of SDMT will be preceded by a learning sequence at both timepoints. We will use parallel versions for all test days.
- Bochumer Matrizentest (BOMAT – advanced; Hossiep/Turck/Hasella, 1999, 1st edition), matrix reasoning. We will administer the BOMAT to measure fluid intelligence (Gf) consisting of 40 items. Parallel versions will be used for the four test days. To create four versions, we divided the original BOMAT versions A and B each into two versions (every second item) with 20 items each. We will use a time-limited version (15 instead of 40 minutes) to avoid a ceiling effect. The total score is calculated by summing the correct solutions, ranging between 0 to 20.

- Working memory will be also assessed with the digit span task, a subtest of the “Wechsler Intelligenztest für Erwachsene” (WIE; (von Aster 2006)). Total scores for digit span forward and backward will be calculated as described in the manual of the WIE. Parallel version will be used for the four test days.

9.3 Assessment of safety outcomes

The following known side effects will be recorded using visual analog scales: headache, gastrointestinal discomfort, dizziness

Adverse events: All clinically relevant (S)AEs occurring after the participant has signed the informed consent until follow up visit will be fully recorded in the participants eCRF. Description of (S)AE, time of onset, duration and resolution. Assessment of intensity, relationship to study drug and measures taken. For documentation of (S)AEs see section 10.

Laboratory parameters: No laboratory parameters will be assessed after screening.

Vital signs: Vital signs (BP, HR) will be taken as described in screening procedures. Blood pressure and heart rate will be used as baseline before intake of study medication, during waiting period, before testing and before end of visit to control for side effects of the medication.

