Description		Screening		Test day 1	P/V or V/P	Test day 2	Wash-out period	Test day 3	V/P or P/V
Day		within 14 days before Visit 2		1		4		12-30	Test day 4
Screening									
• Written informed consent, assignment of the subject number									
• Personal, family and medication history									
• Self-assessment mental health and sleeping habits, MADRS-S, EHI									
• Physical examination									
• ECG, Blood sample									
Treatment periods									
• Electronic intake diary									
• Electronic AE diary (VAS headache, gastrointestinal discomfort, dizziness; free text)	3.5 days				x				x
Wash-out period (8-82 days between V3 and V4)	8-82 days						x		
Test days									
Pre-examination test days									
• Vital signs									
• Flu-like symptoms, common cold symptoms									
• Pregnancy test (Visits 2 and 4)									
• Questionnaire drugs and alcohol consumption during last 3 days resp. past 12 hours									
• Sleep duration last 24 hours									
• AE recording									
• VAS headache, gastrointestinal discomfort, dizziness; VAS tiredness, motivation									
Assignment of the randomization number	5 min		x						
Intake of study medication	5 min		x	x	x		x	x	x
Waiting time (incl. continental breakfast 2 hours after intake of study medication)	4 h		x		x		x		x
Before start of testing									
• AE recording									
• VAS headache, gastrointestinal discomfort, dizziness; VAS tiredness, motivation	15 min		x		x		x		x
Testing Phase – part 1									
• n-Back			x		x		x		x
• Processing speed task SDMT	45 min								
• Digit Span									
Break	15 min		x		x		x		x
Testing Phase – part 2									
• BOMAT	15 min		x		x		x		x
rMT measurement using TMS	15 min	x			x				x
Final Examination									
• AE recording									
• VAS headache, gastrointestinal discomfort, dizziness; VAS tiredness, motivation	15-20 min		x		x		x		x

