3.7 Risks / Benefits

Fampridine application

Although a short term application of 10 mg fampridine twice daily in healthy participants is generally well tolerated (March and Cardi 2009), participants will be informed of the possible risks associated with taking fampridine. Specific risks that participants need to be aware of are listed below:

- The most frequently occurring AEs included dizziness, headache, insomnia and gastrointestinal discomfort. No discontinuations due to AEs were reported in a study with healthy subjects after administration of a single 10 mg dose (Smith, Swan et al. 2010) as well as after 5 days of twice daily fampridine SR 10 mg in healthy subjects (March and Cardi 2009).
- Fampridine is excreted primarily unchanged in the urine (Blight and Henney 2009). Tolerability and incidence of AEs appear to be dose related, occurring more frequently at plasma concentrations > 100 ng/mL (Van Diemen, Polman et al. 1993). We will therefore exclude subjects with renal impairment to avoid higher plasma levels. To assess renal impairment, we will perform creatinine and uric acid levels in plasma.

- Fampridine is excreted primarily through the organic cation transporter 2 (OCT 2). OCT 2 inhibitors or substrates (e.g. Cimetidine, Carvedilol, Propranolol and Metformin) may inhibit elimination of fampridine and increase the risk of adverse events. Subjects with concomitant use of these drugs are excluded from participation.
- Fampridine can cause seizures. We will exclude people with a history of seizures and subjects at risk of lowered seizure threshold due to e.g. sleep deprivation or alcohol withdrawal after alcohol abuse.
- Despite the fact that fampridine at therapeutic and supratherapeutic doses is not associated with QT prolongation in healthy subjects (March and Cardi 2009) we will exclude subjects with any clinically significant ECG abnormalities or history of cardiovascular disease.
- Fampridine might cause nausea and dizziness and have an additive effect with alcohol. Participants will be advised to avoid alcohol, illegal substances, and any medication (especially psychoactive) due to possible interactions during the course of the study.
- An increased risk of bacterial and viral infections is described in the prescribing information. In a study with 47 healthy subjects receiving 10 mg twice daily doses of fampridine SR over 5 days no viral or bacterial infections were reported (March and Cardi 2009).

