4.4 Safety Objectives

The study aims to assess tolerability of study medication in terms of incidence of side effects e.g. headache, gastrointestinal discomfort and dizziness and the rate of AEs.

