10 SAFETY

10.1 Definitions

10.1.1 Adverse Event (AE)

An Adverse Event (AE) is any untoward medical occurrence in a patient or a clinical investigation participant administered a pharmaceutical product and which does not necessarily have a causal relationship with the study procedure. An adverse event can therefore be any unfavorable and unintended sign (including an abnormal laboratory finding), symptom, or disease temporally associated with the use of a medicinal investigational product, whether or not related to the medicinal investigational product.

In this study, the following very common AEs being already described in the prescribing information Fampyra® (version from May 2019) are excluded from recording, but will be measured as possible confounding factor using VAS:

- headache
- gastrointestinal disturbances such as dyspepsia, abdominal pain, constipation and nausea
- dizziness

All other clinically relevant AEs will be fully recorded by describing the AE, time of onset, duration and resolution, assessment of intensity, relationship to study drug and measures taken

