10.3 Documentation

10.3.1 Serious Adverse Events (SAE)

The sponsor's SOPs provide more detail on safety reporting.

During the entire duration of the study all serious adverse events (SAEs) are collected, fully investigated and documented in source documents and electronic case report forms (eCRF). Study duration encompassed the time from when the participant signs the informed consent until the final examination.

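### Adverse events are entered only if judged clinically relevant, an undefined test applied before grading, so the AE rate promised in 4.4 can be understated; VAS symptoms have no incidence rule and sleep duration no analysis

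*Combined protocol and SAP*

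**What the plan says.** Section 4.4 sets the safety objective as tolerability in terms of the "incidence of side effects e.g. headache, gastrointestinal discomfort and dizziness and the rate of AEs". Section 5.3 makes AE recording a safety outcome. Section 10.1.1 defines an AE broadly, as any unfavourable medical event, related to the product or not.

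The recording rules are narrower:

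- 9.3 provides for full recording of "All clinically relevant (S)AEs occurring after the participant has signed the informed consent".
- 10.1.1 takes headache, gastrointestinal disturbances and dizziness out of AE recording and leaves them to VAS. It then states: "All other clinically relevant AEs will be fully recorded by describing the AE, time of onset, duration and resolution".

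Other sections have no such limit. Section 10.3.2 lists the items to collect for adverse events in general, 10.2.2 provides a mild grade, and 10.3.1 says that "all serious adverse events (SAEs) are collected, fully investigated and documented".

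On expected effects, 3.7 states: "The most frequently occurring AEs included dizziness, headache, insomnia and gastrointestinal discomfort". Safety VAS exist for three of these four (5.3, 9.3). For sleep, the Study Schedule lists "Sleep duration last 24 hours" in the test-day pre-examination and 9.4.2 repeats it. Section 7.4 gives under 4 hours of sleep before visit 3 or 5 as an example of an adverse event that prohibits testing.

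Section 11.4.5 names the safety set (at least one dose) and no method.

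**The concern.** Whether an event is clinically relevant is decided before it is entered and graded, and nothing says who decides or by what standard. In healthy volunteers on a short course many events may be mild, and those are the events such a filter is likeliest to remove. A grade 1 category is of limited use if grade 1 events need not reach the log. The quantity at stake is one that 4.4 names.

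Two related gaps affect the same objective. Any AE rate from the log omits three of the four effects that 3.7 calls most frequent, and no cut-off or baseline rule turns their VAS ratings into an incidence. For the fourth, insomnia, there is no severity scale. The sleep duration that is collected is absent from the safety outcomes (5.3), the confounders (5.4), the covariate list (11.4.2) and the safety analysis (11.4.5). Section 7.4 treats short sleep as incompatible with testing, and 11.4.1 analyses completers only. The shortest sleepers can therefore leave the efficacy data, with no planned treatment comparison of sleep in those who remain.

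**Working it through.** **The plan's own figure.** The only computed figure is N = 44 (11.2: paired two-tailed t-test, dz = 0.5, alpha 0.05, power 90%). Exact noncentral-t power is 0.9000 at n = 44 and 0.8931 at n = 43, so it reproduces. It concerns efficacy and does not bear on this point. The documents state no AE or insomnia rate.

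**Text comparison.**

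| Section | Which events are covered | Relevance filter |
|---|---|---|
| 10.1.1, definition | any unfavourable event | no |
| 4.4, objective | rate of AEs | no |
| 10.3.2, items to collect | adverse events | no |
| 10.3.1 | all SAEs | no |
| 9.3 | (S)AEs | yes |
| 10.1.1, recording rule | AEs other than the three VAS symptoms | yes |

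**The four effects named in 3.7.**

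| Effect | AE log | VAS | Rule giving incidence |
|---|---|---|---|
| Headache | excluded | yes | none |
| GI discomfort | excluded | yes | none |
| Dizziness | excluded | yes | none |
| Insomnia | allowed, if judged relevant | no | the log entry |

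Three of the four have a VAS and those three are barred from the log. Insomnia is the reverse.

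**Effect of the filter.** Let p be the true per-period risk of an event and s the share judged clinically relevant. Both are assumptions. Expected entries among 44 participants = 44 × p × s.

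| p | s = 1 | s = 0.75 | s = 0.5 | s = 0.25 |
|---|---|---|---|---|
| 5% | 2.2 | 1.65 | 1.1 | 0.55 |
| 10% | 4.4 | 3.3 | 2.2 | 1.1 |
| 20% | 8.8 | 6.6 | 4.4 | 2.2 |

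The chance that no case is entered is (1 − p × s)^44. At p = 10% it is 0.010 with s = 1 and 0.328 with s = 0.25.

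If s is the same under fampridine and placebo, the recorded risk difference is s × (pF − pP) and the ratio pF/pP is unchanged. With 20% versus 5% and s = 0.5 the difference falls from 15 to 7.5 points and the ratio stays at 4.0.

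**Power, as an illustration under assumed rates only.** The plan specifies no safety test. Inputs: exact two-sided McNemar at 0.05, 44 pairs, events independent within a pair, and the same s in both periods. A pair is discordant towards fampridine with probability a(1 − b) and towards placebo with b(1 − a), where a = s × pF and b = s × pP. Power is summed over all possible discordant counts.

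| True risks | s = 1 | s = 0.75 | s = 0.5 | s = 0.25 |
|---|---|---|---|---|
| 25% vs 5% | 0.675 | 0.484 | 0.244 | 0.034 |
| 30% vs 10% | 0.560 | 0.387 | 0.211 | 0.044 |

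With full recording, 15% versus 5% gives 0.21 and 10% versus 5% gives 0.05. The loss of power is therefore large only if the true difference is large.

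**The case against.** The strongest reply is that this is loose wording in a small proof-of-concept trial whose safety objective is not primary and not powered. Staff are blinded, so the filter probably acts alike in both periods. Section 10.3.2 may be the rule that staff follow in practice. This limits the consequence but does not remove the conflict: 4.4 promises a rate, and equal filtering preserves a ratio but not a rate or a difference.

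A reader might infer several stronger things that the documents do not support:

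- **That the AE rate will be understated.** The passing share s is unknown. At s = 1 nothing is lost. Only that it can be understated is supportable.
- **That the missing insomnia scale lowers the AE rate.** It does not. Insomnia is the only one of the four effects that can enter the log.
- **That sleep problems are captured only through the filter.** The home diary has a free-text field (Study Schedule) and participants enter adverse events there themselves (9.4.3). Sleep duration is asked on test days. Sleep under 4 hours is a logged withdrawal reason (7.4), and drop-outs are described by reason (11.4.1). Tiredness has a VAS and is a covariate (11.4.2). What is missing is a severity scale and an analysis.
- **That SAEs may be lost.** Section 9.3 attaches the filter to (S)AEs but refers to section 10 for their documentation. There 10.3.1 collects all SAEs and 10.4.1 requires all to be reported. An SAE judged not clinically relevant is hardly conceivable. The wording should be aligned, but data loss is not plausible.
- **That the power figures measure this trial.** They rest on assumed rates and an unplanned test, and they address a single symptom, not the overall AE rate.

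**Conclusion.** The point holds in a limited form. Sections 9.3 and 10.1.1 apply an undefined pre-grading filter that conflicts with the protocol's own AE definition, 10.3.2 and 10.3.1. Followed as written, it can lower the recorded AE rate and cannot raise it. The rate is multiplied by s, somewhere between 0 and 1, and the documents give no means of narrowing that range.

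Independently of the filter, the log omits three of the four most frequent effects, and no rule supplies the incidence that 4.4 promises for them. Insomnia lacks a severity scale and sleep duration lacks an analysis; these are gaps in measurement and reporting and do not themselves bias the AE rate.

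The stated safety objective is affected. The sample size and the primary test are not.

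**What to change.** 1. Delete the clinical-relevance qualifier in 9.3 and in the recording rule of 10.1.1. Every AE other than the three VAS symptoms is then entered and graded under 10.2.2, and every SAE is entered as in 10.3.1.
2. Prespecify how VAS ratings of headache, gastrointestinal discomfort and dizziness become incidence: the cut-off, the handling of the pre-dose rating, and which diary and test-day ratings count. Report these incidences by treatment beside the AE rate. Without this step, deleting the filter still leaves the three symptoms out of any rate.
3. In 5.3 and 11.4.5, add sleep duration at visits 3 and 5 as a tolerability outcome. Compare fampridine with placebo in all dosed participants with data, not only completers.
4. Optionally, add an insomnia item to the existing electronic diary and test-day VAS.

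The cost is wording in a few sections, one short analysis rule, some extra mild-AE entries and, if taken up, one more rating item. No visit is added. The reported AE count will be higher.
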